6.7 Financial Obligations and Compensation

There is no charge for participation in this study. Vaccines and related preparation and administration charges and all study-related labs will be provided without cost to the participant. To compensate Aim 2: Vaccine Evaluation participants for their time and transportation expenses related to study participation, participants will receive \$100 (or equivalent voucher/gift card) at Month 7 and \$75 (or

equivalent voucher/gift card) at Month 24.

6.8 **Informed Consent Process**

Informed consent will be obtained from each patient (of age of majority) according to the approved procedures of the institutional review board (IRB) or Ethics Committee at each participating institution. Consent of the parent/guardian and assent of the patient will be obtained for each minor participant according to the policies and procedures in place at each participating institution and according to the laws in the state where the informed consent is being signed. The original consent form will be placed in the medical record. A copy will be given to the participant and a copy will be filed with the research record.

7.0 **CRITERIA FOR EVALUATION AND ENDPOINT DEFINITIONS**

7.1 **Evaluable Patients**

Aim 1 (Survey): A subject will be considered evaluable if they complete the survey item indicating HPV vaccine initiation/non-initiation and for whom medical record abstraction data is submitted as described in Section 4.3.

Aim 2 (Vaccine Evaluation): A subject will be considered evaluable for the primary (immunogenicity) aim if they are seronegative for HPV-16 and/or HPV-18 at baseline, complete all 3 HPV vaccine doses within the specified administration windows (Section 5.4.4), have evaluable Month 7 Anti-HPV 4cLIA (for patients enrolled on or before 3-1-16) or 9cLIA (for patients enrolled after 3-1-16) results that were drawn within the acceptable window (Section 5.4.6), and for whom medical record abstraction data is submitted as described in Section 5.3. Safety data will be reported on all eligible subjects who receive at least one dose of vaccine, regardless of whether they are evaluable for the additional study aims.

7.2 **Primary Endpoints**

Aim 1 (Survey):

1. HPV vaccine non-initiation

Aim 2 (Vaccine Evaluation):

1. HPV antibody titers (Anti-HPV 4cLIA [for patients enrolled on or before 3-1-16] or 9cLIA [for patients enrolled after 3-1-16] [Geometric Mean Titers; Seropositivity] (Day 1, Month 7, and Month 24) [Immunogenicity]
2. Vaccine Report Card (participant/parent diary of adverse events, collected for 7 days (for patients enrolled after 3-1-16) or 14 days (for patients enrolled on or before 3-1-16) following each vaccine dose, and Adverse Events/Research-Related Problems Reporting Forms [Safety/tolerability]

7.3 **Schema – Aim 1: Survey**

Aim 1: Survey

[Protocol v3, 8/17/15: Accrual goal for Aim 1 met, enrollment to survey closed]

Requirement	Pre-Entry	Study Entry
Verification of eligibility (Protocol Section 3.1)	X	
Informed consent/assent		X
Registration		X
Medical record abstraction: - Medical Record Review Form (Appendix 1) - Intensity of Treatment Rating Scale (Appendix 2)		X
Survey completion (Appendix 3)		X

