8.0 STATISTICAL METHODS

8.1 Sample Size

Aim 1 (Survey): A sample size of 1090 eligible subjects is required to address Specific Aim 1. We have chosen this sample size based on our preliminary study (Section 2.9), from which we can assume that 90% (n=981) of those approached will participate in the survey. A sample of 981 survey participants for Specific Aim 1 will provide 80% power to reject the null hypothesis that the prevalence (p) of HPV vaccine initiation is ≤ 0.4 if the true p is at least 0.44 (one-sided test, Type I error=0.05). It will also provide a 2-sided 95% confidence interval (CI) of sample $p \pm .061$ if true $p=0.4$.

[Protocol v3, 8/17/15: Accrual goal for Aim 1 met, enrollment to survey closed]

Aim 2 (Vaccine Evaluation):

qHPV Vaccine Cohort (patients enrolled on or before 3-1-16): Based on national vaccine initiation rates and our preliminary data (Section 2.9),⁴⁰ we conservatively assume that 60% (n=589) of the 981 survey participants will have not initiated the HPV vaccine. Based on our data (Section 2.9) and prior trials,^{30,31,135} we conservatively assume that of the non-vaccinated survey participants, 60% (n=353) will agree to receive the vaccine, 96% (n=339) will be seronegative at baseline (Intent to Treat [IT] sample), and 92% (n=312) will complete all 3 doses, yielding 312 (Per-Protocol [PP]) subjects who will have received all 3 doses of qHPV vaccine for examining Aim 2.1. This sample size was calculated using the mean GMT and SD reported by Merck & Co.²⁸ for healthy males and females aged 9-15 years and 16-26 years as the historical healthy population. The following assumptions were made: i) cancer survivors were similarly distributed in regard to immunogenicity with the same SD as in this healthy population; ii) margin of equivalence (E) was $\frac{1}{2}$ of the mean GMT of the healthy population (Table 7). Using the method of Korn and Freidlin¹³⁶ for sample size calculations using historical controls, a total of 312 subjects (72 younger females, 77 older females, 82 younger males, and 81 younger males) will provide 80% power to demonstrate non-inferiority with respect to anti-HPV-16, and/or -18 GMT in cancer survivors compared to the healthy population assuming a one-sided t-test, Type I error =0.00312 (for an overall Type I error =0.025), and margin of equivalence (E) shown in Table 7 by sex and age for each vaccine type.

Table 7. Sample Size for Aim 2 (Vaccine Evaluation)

		Females								

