8.2.2. Aim 2 (Vaccine Evaluation)

8.2.2.1. Determine immunogenicity of qHPV and 9vHPV vaccine 1 month following the third and final vaccine dose

The primary analytic approach will be per-protocol (PP)³⁰ analysis; intention to treat analysis will also be conducted. The evaluation will be completed separately for the qHPV and 9vHPV cohorts. The sample size is powered to determine whether vaccine-induced anti-HPV-16 and -18 neutralizing antibody response in cancer survivors is comparable to the age- and sex-matched general population (Table 7); PP immunogenicity population includes participants who are seronegative for the oncogenic vaccine components of primary interest (HPV-16, -18) on Day 1, complete all three vaccine doses within the protocol-specified time frames, and have immunogenicity data available at the time of analysis. Each vaccine component will be analyzed separately, and we will adjust for intensity of treatment. Anti-HPV-6 and -11 (and in the 9vHPV cohort, Anti-HPV-31, -33, -45, -52, and -58) response will also be explored. The primary outcome of interest is GMT. We will also assess seropositivity rates among cancer survivors. Seropositivity (binary variable) is defined as: qHPV cohort: Anti-HPV-6, -11, -16, and -18 titer ≥ 20 , 16, 20, and 24 mMU/ml respectively;³⁰ 9vHPV cohort: Anti-HPV-6, -11, -16, -18, -31, -33, -45, -52, and -58 titer ≥ 30 , 16, 20, 24, 10, 8, 8, 8, and 8 mMU/ml, respectively.⁶⁹

Outcome measure (GMT): Using the historical healthy population for qHPV²⁸ and 9vHPV⁶⁹ respectively, a multiplicity-adjusted 95% 2-sided confidence intervals for the ratio of mean GMT for HPV-16 and -18 in the cancer and healthy population will be computed. If the lower 95% limit is greater than 0.5, immunogenicity in cancer survivors will be considered non-inferior.³⁰

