Outcome measure: (seropositivity) [Exploratory only; study is not powered for this]: The percent of seropositive participants at Month 7 will be compared to the percent of age- and sex-matched seroconverted individuals in the historical healthy population for each of 2 vaccine components. Two one-sided tests of noninferiority (for each of 2 HPV types) will be conducted for each age-sex group at the 0.025 level (multiplicity adjusted) according to the methods of Miettinen and Nurminen.¹³⁷ Seroconversion in cancer survivors will be considered non-inferior if the lower 95% CI for the difference in percent seropositive between the healthy and cancer population is <5 percentage points.³⁰ The above analyses will be conducted for PP and IT samples. Although not powered to detect non-inferiority for HPV-6 and -11 (and in the 9vHPV cohort, HPV-31, -33, -45, -52, and -58), we will also conduct similar analyses for GMT and seropositivity for these types.

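### Sections 7.1 and 8.2.2.1 give different baseline-serostatus rules for the per-protocol set, and neither limits each HPV type's analysis to subjects seronegative to that type

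*Combined protocol and SAP*

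**What the plan says.** - **Section 7.1** makes a subject evaluable for the primary immunogenicity aim if "seronegative for HPV-16 and/or HPV-18 at baseline, complete all 3 HPV vaccine doses within the specified administration windows", with an in-window Month 7 titre and abstracted records. Taken literally, seronegativity to one of the two types is enough.
- **Section 8.2.2.1** states that the "PP immunogenicity population includes participants who are seronegative for the oncogenic vaccine components of primary interest (HPV-16, -18) on Day 1", with all doses on schedule and titres available. The natural reading is both types. It adds: "Each vaccine component will be analyzed separately, and we will adjust for intensity of treatment". It does not say that the analysis set changes with the component.
- **Section 8.1** plans that, of 353 vaccinated, "96% (n=339) will be seronegative at baseline (Intent to Treat [IT] sample), and 92% (n=312) will complete all 3 doses". It does not say to which type or types the 96% refers.
- **Section 8.2.2.1, seropositivity:** the Month 7 percentage is "compared to the percent of age- and sex-matched seroconverted individuals in the historical healthy population". For HPV-6, -11 and the five added 9vHPV types, "we will also conduct similar analyses for GMT and seropositivity for these types".
- **Section 3.2** screens on reported vaccination history, not serostatus, so seropositive people can enrol.
- **Sections 5.2 and 8.1** replace non-evaluable participants and close a stratum on its count of evaluable participants.

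**The concern.** Take a subject who is HPV-16 seropositive and HPV-18 seronegative on Day 1. Under 7.1 the subject is evaluable, and no text removes them from the HPV-16 GMT. Under 8.2.2.1, read as both types, the subject is lost from both analyses, including HPV-18, where their data are valid. These are alternative consequences of two readings; they cannot both happen.

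Under the first reading, pre-existing antibody could be credited to the vaccine in a comparison whose margin is a GMT ratio of 0.5. The exploratory types have a separate gap. Neither rule looks at baseline serostatus for HPV-6, -11, -31, -33, -45, -52 or -58. Yet the seropositivity comparator is people who seroconverted, which Section 2.4.1 describes as negative before vaccination and positive after. A survivor already positive on Day 1 would be expected to count as a Month 7 success whatever the vaccine did. The Month 24 persistence analysis in 8.2.2.4 uses per-protocol subjects and inherits the ambiguity.

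**Working it through.** **1. The plan's own figures.** The funnel in 8.1 reproduces: 981 × 0.60 = 589; × 0.60 = 353; × 0.96 = 339; × 0.92 = 312. The per-test level is 0.025/8 = 0.003125, against the stated 0.00312. A one-sample noncentral t calculation (one-sided 0.00312, power 0.80, E and SD from Table 7) gives these sizes for HPV-16/HPV-18:

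| Stratum | Computed | Table 7 |
|---|---|---|
| Younger females | 70/68 | 72/69 |
| Older females | 79/61 | 77/58 |
| Younger males | 71/79 | 72/82 |
| Older males | 71/80 | 72/81 |

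The larger value per stratum sums to 70 + 79 + 79 + 80 = 308, against 312. The design is therefore understood well enough to test.

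**2. Yield under each reading.** Assume 96% seronegative to each type and independence between types (the documents state neither):
- either type: 353 × (1 − 0.04²) × 0.92 = 324
- type-specific: 353 × 0.96 × 0.92 = 312 per type
- both types: 353 × 0.96² × 0.92 = 299

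Under these assumptions only the both-types reading falls short of 312.

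**3. Effect on the GMT if 7.1 governs.** Let f be the share of a type's set that was seropositive to it on Day 1, and r their Month 7 titre relative to seronegative subjects. The GMT is multiplied by r^f. The value f = 4% is the complement of the plan's 96%; r is assumed.
- f = 4%: 2^0.04 = 1.03; 5^0.04 = 1.07
- f = 8%: 10^0.08 = 1.20

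The 8% is an extreme case in which every seropositive subject is in the two older strata: 0.04 × 312 / (77 + 81) = 7.9%. At 4%, a pooled ratio of 0.50 corresponds to a seronegative ratio of 0.50/1.028 = 0.486 (r = 2) or 0.50/1.066 = 0.469 (r = 5).

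**4. Effect on type I error.** Set the true seronegative ratio at 0.5, n = 77 (older females) and log-SD s = 1.0 to 1.3 (assumed). The mixture shifts the log mean by f·ln r and also widens the spread: s′² = s² + f(1 − f)(ln r)². The normal approximation is P(Z > 2.734 − f·ln r·√77 / s′). For f = 4%, r = 5, s = 1.0: the shift is 0.0644, s′ = √(1 + 0.099) = 1.049, and the error is 0.014. Simulating the one-sample t-test on the mixture (400,000 runs per scenario) gives:

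| f | r | Per-test error, s = 1.3 to 1.0 |
|---|---|---|
| 0 | – | 0.003 |
| 2% | 2 to 5 | 0.004–0.006 |
| 4% | 2 | 0.005–0.006 |
| 4% | 5 | 0.010–0.012 |
| 8% | 10 | 0.045–0.069 |

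A separate simulation put the top of the 4%, 5-fold row at 0.013. Read as log-normal, Table 7 implies log-SDs of 0.86–0.95. The simpler formula without the variance term then gives 0.006–0.016 at 4% across the eight cells, which is the same order.

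**The case against.** The strongest reply is that 7.1 says who is evaluable for the aim and does not assign anyone to a particular type's GMT. Section 8.1 uses the same connective type by type: the sample "will provide 80% power to demonstrate non-inferiority with respect to anti-HPV-16, and/or -18 GMT in cancer survivors compared to the healthy population". So 7.1 may mean evaluable for 16, for 18, or for both. Section 8.2.2.1 defines the primary analysis set, and whether it is read as both types or type by type, it keeps an HPV-16-seropositive subject out of the HPV-16 GMT. The 8.1 funnel also drops the 4% before either sample is formed. If the 96% means negative to both types, the share positive to one tested type is at most 4%, and less if positives split between types.

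Much of this stands. The bias is conditional on 7.1 governing, and 4% is a planning figure, not an observed share in any analysis set. The direction for GMT also rests on two facts the documents do not supply: higher Month 7 titres in prior-positive subjects, and a seronegative historical reference. The seropositivity comparison is labelled exploratory, and the additional types are not powered, so that gap touches no primary conclusion. Section 8.2.2.1 also uses seroconversion loosely for the survivors themselves.

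The reply does not remove the conflict. The type-specific intention has to be inferred, and two analysts could build different sets from the same text.

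A reader might go further and infer that the primary test is badly inflated, for instance to 0.13 at 8% seropositive and 10-fold titres. That figure shifts the mean but leaves the SD at 1.0. The mixture adds variance 0.08 × 0.92 × (ln 10)² = 0.39, raising the SD to 1.18; simulation then gives about 0.07. The scenario also needs all seropositives in the older strata, all positive to the same single type, and a 10-fold ratio, none of which the documents support.

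**Conclusion.** The point holds as a conflict between two definitions of one analysis set, with no type-specific restriction to settle it. If 7.1 governs, the HPV-16 and HPV-18 GMT tests can include subjects already seropositive to the tested type. On the two unstated assumptions about titres and the reference, this leans toward non-inferiority. At the plan's 4% with 2- to 5-fold titres, the GMT rises 3–7% and per-test error is about 0.005–0.013 against 0.003; in the extreme 8%, 10-fold case it is about 0.05–0.07. It would matter mainly for a result close to 0.5 or a stratum with more prior infection. Section 2.2 reports higher infection prevalence in females aged 20–24 (44.8%) than 14–19 (24.5%). That makes concentration in older strata plausible, but any-type infection is not type-specific seropositivity.

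If 8.2.2.1 governs and means both types, the cost is lost valid data rather than bias. The missing restriction for the other seven types remains under either rule, for exploratory analyses only. The documents do not support saying that the primary conclusion is biased; they support saying that the text permits it and should not. The change should be made, but the trial does not stand or fall on it.

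**What to change.** Put one rule in 7.1 and 8.2.2.1: for each HPV type, the per-protocol set is the subjects seronegative to that type on Day 1 who received all three doses in window and have an in-window Month 7 titre. Then:
- apply it to both GMT and seropositivity, for every type in each cohort, and carry it through to the Month 24 analysis;
- count stratum targets and replacements on the HPV-16 and HPV-18 sets;
- state in 8.1 which type or types the 96% covers;
- confirm that the historical reference for each vaccine carries the same serostatus restriction.

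The cost is wording and a check of the reference. Day 1 type-specific titres are already scheduled, so no new sample is needed. A few subjects leave one type's analysis, about 3 per stratum at 4% (0.04 × 77 = 3.1). Compared with the both-types reading, some return to the other type's analysis.

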3.3 Exclusion Criteria: Aim 2 (Vaccine Evaluation)

- 3.3.1 Allergy to any component of the HPV vaccine including yeast and aluminum
- 3.3.2 Thrombocytopenia (platelet count <50K) or coagulation disorder that would contraindicate intramuscular injection
- 3.3.3 Transfusion of blood products or intravenous immune globulin within 3 months of study entry
- 3.3.4 Female, and a) currently pregnant or lactating, or b) of childbearing potential and unwilling to avoid pregnancy during the vaccine phase of study (beginning at Day 1 and continuing until at least 4 weeks after all 3 vaccine doses have been administered).

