8.2.2.3. Determine the safety/tolerability of the qHPV and 9vHPV vaccine in cancer survivors

In the IT sample, the number of vaccine-associated AE within 7 (for 9vHPV) or 14 (for qHPV) days of each dose will be compared to those reported for the age- and sex-matched general population: % of subjects with injection site AEs (e.g., pain, erythema), % of subjects with systemic AEs (e.g., fever, syncope, headache, hives, rashes, diarrhea), % of subjects with serious AEs (e.g., life-threatening, result in persistent disability or death). Overall cohort: % of subjects who discontinue vaccine related to AE. AEs will be summarized descriptively as frequencies and percentages by type (injection site, systemic, serious), by vaccine dose (i.e., #1, #2, #3), and across all vaccine doses. Chi-square and exact tests will be used for comparison depending on the rarity of events. Our smallest PP subsample of 72 young females will provide 80% power to detect a difference of 0.0485 in AE rates if true rate=0.01, and a difference of 0.1068 if the true rate=0.85. For the largest PP subsample of 82 young males, the corresponding detectable differences are 0.0415 and 0.1021. For the entire PP sample of 312, the corresponding differences are 0.0189 and 0.0534. Type I error=.05 is assumed for each comparison.

8.2.2.4. (Exploratory sub-aim): Evaluate the persistence of antibody response at 2 years post vaccine initiation and identify clinical/host factors influencing response persistence.

Outcome measure (GMT): We will calculate mean GMT and 2-sided 95% CI for HPV-16 and -18 at Month 24 following vaccine initiation for PP subjects and compare them to age-, sex-, and time-matched means in the historical healthy population.²⁸ Cancer survivors will be considered to have non-inferior persistence of antibody response to a subtype at a time point if the lower 95% confidence limit for the ratio of GMT in cancer survivors to historical healthy population is $\geq 50\%$.³⁰

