9.3.3. Toxicity Management

Any symptoms that occur will be managed according to good medical practices and clinical judgment of the site investigator. Toxicities related to the vaccine will be monitored using the *Toxicity Grading Scale for Healthy Adult and Adolescent Volunteers Enrolled in Preventive Vaccine Clinical Trials*, U.S. Department of Health and Human Services, Food and Drug Administration, Center for Biologics Evaluation and Research, September 2007 (Tables 9.3.2, 9.3.3, and 9.3.4). Toxicities will generally be considered potentially vaccine-associated if their onset occurs within 7 days after receipt of a study vaccine dose. If evaluated, the toxicity should be documented on the Adverse Events/Research-Related Problems Reporting Form (AERF) within 2 working days of the evaluation. All subjects will be followed for the reporting of toxicities for 14 days following each vaccine dose. In addition, any severe or unexplained toxicity occurring after the 14 days of follow-up brought to the attention of the investigator will be evaluated for possible vaccine-association, and documented on the AERF within 2 working days of the evaluation if found to be possibly, probably, or definitely related to the vaccine. Toxicities will not be considered vaccine-associated AEs if clearly recognized alternative etiologies are identified. Alternative explanations for clinical abnormalities must be sought prior to study vaccine discontinuation.

Therapeutic interventions that may interfere with evaluation of the safety/tolerability of the vaccine should be avoided during the indicated timeframes unless medically necessary. These include a) any live attenuated vaccine administered within 28 days of any HPV vaccine dose; b) any subunit or killed vaccines (e.g., influenza, pneumococcal, antigen injections for allergy treatment) within 14 days of any HPV vaccine dose.

General toxicity management:

- If a subject develops a persistent \geq Grade 3 clinical toxicity, the subject will not be permitted to participate in this study until the toxicity has resolved to \leq Grade 1.
- All \geq Grade 3 clinical toxicities occurring within 14 days following any vaccine dose, and their

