proposed management, must be reported to the coordinating center using the AERF within 2 business days of the site's awareness of the event, regardless of relatedness. Clinical toxicities not identified in Tables 9.3.2, 9.3.3, and 9.3.4 should be graded according to the Common Terminology Criteria for Adverse Events v4.0 (<http://safetyprofiler-ctep.nci.nih.gov/CTC/CTC.aspx>).

9.3.4. Pregnancy: Sexually active females of childbearing potential will be instructed to use contraception throughout the 6-month period when the vaccine is administered. Participants will be queried prior to each dose to determine if there is a possibility of pregnancy; if so, a pregnancy test (urine or blood as per local institutional preference) will be obtained prior to vaccine administration. If positive, the participant will be withdrawn from receiving further vaccine on the study. Any pregnancy occurring during the vaccine phase of the study (i.e., Vaccine Day 1 through 4 weeks after all 3 vaccine doses have been administered) will be reported to the study coordinating center. There are no data indicating an association of adverse pregnancy outcomes or adverse effects of the developing fetus with the vaccine. Thus, if a vaccine dose is administered during pregnancy, no intervention is indicated other than withholding further doses and reporting as specified. The patient should be followed by the participating site for pregnancy outcome data (e.g., termination, miscarriage, pre-term or full-term delivery, fetal death/stillbirth, complications, single vs multiple birth, condition of infant(s), presence of congenital anomalies, etc.), which should be reported to the study coordinating center when available. The study coordinating center will report the pregnancy, and later the pregnancy outcome (with de-identified subject information only), as follows: **gHPV vaccine recipients (patients enrolled on or before 3-1-16)**: Merck Worldwide Product Safety; [contact]. **9vHPV vaccine recipients (patients enrolled after 3-1-16)**: Gardasil^{®9} Pregnancy Registry maintained by Merck (URL: www.merckpregnancyregistries.com/gardasil9; [contact]; [contact]) and Merck Worldwide Product Safety; [contact].

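### Section 7.1 limits the reported safety set to eligible vaccinated subjects, and Section 8.2.2.3 uses a different set; both should be everyone who received a dose

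*Combined protocol and SAP*

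**What the plan says.** The plan describes the safety population in several places, and they differ.

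- **Section 7.1 (reported safety set):** "Safety data will be reported on all eligible subjects who receive at least one dose of vaccine", whether or not they can be evaluated for the other aims. Subjects must be eligible and must have had at least one dose.
- **Section 3.3 (what makes a subject ineligible for Aim 2):** the first exclusion is "Allergy to any component of the HPV vaccine including yeast and aluminum". The others are thrombocytopenia or a coagulation disorder, recent transfusion or immune globulin, and pregnancy, lactation or unwillingness to avoid pregnancy.
- **Section 8.2.2.3 (adverse event comparisons):** "In the IT sample, the number of vaccine-associated AE within 7 (for 9vHPV) or 14 (for qHPV) days of each dose" is compared with general-population figures. Discontinuation because of an adverse event is instead given for an overall cohort that is not defined.
- **Section 8.1 (the only description of the IT sample):** after "60% (n=353) will agree to receive the vaccine", the chain continues "96% (n=339) will be seronegative at baseline (Intent to Treat [IT] sample".
- **Section 9.3.3 (follow-up):** "All subjects will be followed for the reporting of toxicities for 14 days following each vaccine dose".
- **Section 9.3.4 (pregnancy):** "if a vaccine dose is administered during pregnancy, no intervention is indicated other than withholding further doses and reporting as specified".

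No section says what happens in the safety analysis to a subject found ineligible after vaccination.

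**The concern.** For safety, the natural denominator is everyone exposed. Three of the four Aim 2 exclusions exist wholly or partly for safety, so a subject vaccinated in breach of one may be at higher risk of a reaction. A reaction can also be what reveals an allergy not known at entry. If eligibility is then reassessed, the literal 7.1 sentence puts the subject who reacted outside the reported set. Any such loss would tend to favour the hypothesis in Section 1.0 that the vaccines are safe and well tolerated. The trial is single-arm, so no control group loses subjects in the same way.

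Late discovery is possible under the plan's own procedures. No platelet count is among the study laboratory tests (Sections 5.4.6 and 7.4). Pregnancy is tested only when the participant's answers suggest that it is possible (Section 5.4.7.2). The cancer treatment summary, whose dates bear on the 12-to-60-month criterion, is scheduled for abstraction at Month 7, after all three doses (Section 7.4).

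**Working it through.** **Step 1. Compare the sets.**

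| Place | Set | Eligibility limit? | Serostatus limit? |
|---|---|---|---|
| 7.1, safety data | at least one dose | yes | no |
| 8.2.2.3, AE comparisons | IT sample | not stated | yes, through 8.1 |
| 8.2.2.3, discontinuation for AE | overall cohort, undefined | not stated | not stated |
| 9.2, DSMC percentages | subjects | no | no |
| 9.3.2 and 9.3.3, SAEs and toxicity | all SAEs, all subjects | no | no |

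Neither of the two sets that feed the study's own safety results (7.1 and the AE comparisons in 8.2.2.3) is everyone exposed. The only rows clearly free of both limits are the monitoring provisions in Section 9.

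**Step 2. Reproduce the plan's figures.** The Section 8.1 chain is 981 × 0.60 = 588.6 (589); 589 × 0.60 = 353.4 (353); 353 × 0.96 = 338.9 (339); 339 × 0.92 = 311.9 (312). It reproduces. The detectable AE differences in 8.2.2.3 also reproduce with an exact one-sample binomial test. At a true rate of 0.01 and upper-tail alpha of 0.05, power is 0.800, 0.800 and 0.799 for n = 72, 82 and 312. At 0.85 and upper-tail alpha of 0.025, it is 0.800, 0.800 and 0.801. These figures use per-protocol counts, so redefining the safety set does not alter them.

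**Step 3. Weight of one subject.**

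- 1/353 = 0.28% of planned vaccinees
- 1/254 = 0.39% of the qHPV cohort enrolled by 3-1-16 (Section 8.1)
- 1/200 = 0.5% of the planned 9vHPV cohort

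**Step 4. Range for the shift in a rate.** The documents give no count of subjects vaccinated despite an exclusion, so k of 353 is an assumption. Take an extreme case: all k have an event whose rate is 1% in the rest. Including them raises the rate by [0.01 × (353 − k) + k]/353 − 0.01 = 0.99k/353.

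| k (assumed) | Share of 353 | Rise in rate, percentage points |
|---|---|---|
| 1 | 0.28% | 0.28 |
| 2 | 0.57% | 0.56 |
| 7 | 1.98% | 1.96 |
| 18 | 5.10% | 5.05 |

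The shift can also go the other way. For a common reaction at 85% in the rest and none in the k subjects, including them lowers the rate by 0.85k/353: 0.24 points for k = 1 and 1.69 for k = 7.

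**Step 5. A rare serious event in the 9vHPV cohort.** Assume that 2 of 200 are found ineligible and that nobody else has a serious event.

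- Neither has one: 0/198 against 0/200, with no practical difference.
- One has one: 0/198 (exact 95% upper limit 1.85%) against 1/200 = 0.5% (upper limit 2.75%).
- Both have one: 0/198 against 2/200 = 1.0%.

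**Step 6. The serostatus restriction, for scale.** As Section 8.1 describes it, the IT sample omits 353 − 339 = 14 planned vaccinees, or 14/353 = 4.0%, from the AE comparisons. Editing 7.1 alone would leave this in place.

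**The case against.** The strongest objection is that Section 9 already covers these people. All SAEs are reported (9.3.2), and the manufacturer receives every serious event whatever its cause (9.3.2.1.2). All subjects are followed for toxicity, and Grade 3 or higher toxicities within 14 days go to the coordinating center whatever their relatedness (9.3.3). DSMC percentages are per subject (9.2), and vaccine-phase pregnancies are reported (9.3.4). This stands. A reader might infer from 7.1 that such events escape safety reporting altogether; the documents do not support that. What remains is that the study's reported safety results could differ from what the DSMC saw.

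Second, the plan contains no procedure for removing subjects after the fact. Eligibility is verified before entry and the treating clinician gives clearance (Sections 5.2 and 7.4). The 7.1 sentence is there to widen the safety set beyond evaluable subjects, and *eligible* may loosely mean enrolled. That is a fair reading, and the text should not be called a rule to drop exposed cases. But the word is there, nothing overrides it, and if only enrolment was meant, deleting it loses nothing.

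Third, a reader might take Section 9.3.4 to mean that anyone dosed during pregnancy falls out of the set. That is also too wide. A woman who conceives after entry was eligible and stays in. The pregnancy example fits only pregnancy or lactation already present at entry.

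Fourth, it is not shown that each excluded group reacts more often. Section 9.3.4 says there are no data linking the vaccine to adverse pregnancy or fetal outcomes. The direction of bias is therefore plausible and not established.

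**Conclusion.** The point holds for the reported safety results. Read literally, Section 7.1 leaves out subjects found after vaccination to have breached Section 3.3, and no other section defines the safety analysis set as everyone exposed. It does not hold for safety surveillance.

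The size is unknown and probably small. The rates shown rest on assumed counts, and the shifts of several points need both many ineligible vaccinees and an event in every one. The practical risk lies with rare serious events, where a single case can separate a report of none from a report of one. Immunogenicity results, sample size and stated power are unaffected. The inconsistency between 7.1 and 8.2.2.3 needs no assumption about eligibility breaches: it follows from the text, given that the Section 8.1 description of the IT sample is the one meant in 8.2.2.3.

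**What to change.** 1. In Section 7.1, delete *eligible*, so that the safety set is all subjects who receive at least one dose.
2. State there that subjects found ineligible after vaccination stay in the safety set, and flag or list them with the criterion breached and any events.
3. In Section 8.2.2.3, replace the IT sample with this same set for the adverse event analyses, whatever the baseline serostatus, and say that the overall cohort used for discontinuations is also this set.

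The cost is a short text amendment in two sections. The data are already collected under Section 9, so no new data are needed and no sample size changes. Item 1 alone would not be enough, because the comparisons in 8.2.2.3 would still run on the IT sample.
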